6.3.1 Potential drug-induced liver injury IMP discontinuation criteria

Subjects with potential drug-induced liver injury (PDILI) must be assessed to determine if IMP must be discontinued. In addition, all concomitant medications and herbal supplements that are not medically necessary should also be discontinued.

The PDILI criteria below require immediate and permanent discontinuation of IMP:

- Subjects with either of the following:
 - ALT or AST $\geq 5xULN$
 - ALT or AST $\geq 3xULN$ and coexisting total bilirubin $\geq 2xULN$

The PDILI criterion below requires immediate discontinuation of IMP:

- Subjects with ALT or AST $\geq 3xULN$ who exhibit temporally associated symptoms of hepatitis or hypersensitivity. Hepatitis symptoms include fatigue, nausea, vomiting, right upper quadrant pain or tenderness. Hypersensitivity symptoms include fever (without clear alternative cause), rash, or eosinophilia (ie, $>5\%$).

If a nondrug-related cause for the symptoms can be confirmed, these subjects may resume IMP administration after discussion with the responsible UCB physician, but only when the requirements for rechallenge with IMP as provided in [Section 11.6.1.2](#) are followed.

The PDILI criterion below allows for subjects to continue on IMP at the discretion of the investigator.

- Subjects with ALT or AST $\geq 3xULN$ (and $\geq 2x$ baseline) and $<5xULN$, total bilirubin $<2xULN$, and no eosinophilia (ie, $\leq 5\%$), with no fever, rash, or symptoms of hepatitis (eg, fatigue, nausea, vomiting, right upper quadrant pain or tenderness).

Evaluation of PDILI must be initiated as described in [Section 11.6.1](#). If subjects are unable to comply with the applicable monitoring schedule, IMP must be discontinued immediately.

Investigators should attempt to obtain information on subjects in the case of IMP discontinuation to complete the final evaluation. Subjects with PDILI should not be withdrawn from the study until investigation and monitoring are complete. All results of these evaluations and observations, as well as the reason(s) for IMP discontinuation and subject withdrawal (if applicable), must be recorded in the source documents. The eCRF must document the primary reason for IMP discontinuation.

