13.4.1 Safety analyses

Adverse events will be reported in frequency tables as the number and percentage of subjects reporting TEAEs by treatment group. Additionally, frequency tables for serious TEAEs, non-serious TEAEs, TEAEs leading to discontinuation of study medication, TEAEs by intensity and TEAEs by relationship to treatment will be provided by treatment group.

Descriptive statistics on change from Baseline in laboratory data, including hormone status, will be summarized by visit and treatment group. Post-Baseline clinical significant abnormalities will be presented by treatment group.

Vital signs variables and their change from Baseline will be presented using descriptive statistics by visit and treatment group. The number and percentage of subjects meeting orthostatic hypotension criteria will also be presented.

ECG and its change from Baseline will be presented using descriptive statistics by visit and treatment group. The number and percentage of subjects with post-Baseline clinical significant abnormalities will be presented by treatment group.

Body weight, height, and BMI and their change from Baseline will be presented using descriptive statistics by visit and treatment group. Clinically significant values will be reported.

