3.2.3 Visit mapping

The visits are planned as shown in the Protocol Table 5-1 Schedule of assessments. These visit windows were revised for the purpose of identifying important protocol deviations at visits 2, 7 and 8:

Visit	Day	Visit Window
Visit 1 (Screening)	Day -28 to Day -1	
Visit 2 (Baseline)	Day 0	+5 Days
Visit 3	Day 1	+5 Days
Visit 4	Day 8	± 1 Day
Visit 5	Day 15	± 1 Day
Visit 6 (Start of Maintenance)	Day 22	± 2 Days
Visit 7	Day 50	± 5 Days
Visit 8	Day 78	± 5 Days
Visit 9 (EoM)	Day 106	± 2 Days
Visit 10	Day 110	Visit 9 + 4 days
Safety Follow-Up	30 Days after End of Taper Period	

Analysis by visit will be done as documented in the eCRF, i.e., no visit correction will be conducted due to deviations from scheduled time points.

Assessments at premature withdrawal of the study are documented in the eCRF pages of Visit 9 (EoM/ Withdrawal). For data listings, assessments of Withdrawal Visit and of Visit 9 as scheduled will be presented separately as

- Premature Withdrawal for subjects who prematurely terminated the study
- Visit 9 (EoM) for subjects who completed the study.

Unscheduled assessments may be recorded during the study. Information collected in the log forms (e.g., AEs and concomitant medications) is included in the analysis. However, assessments at unscheduled visits will not be considered in the by-visit analysis unless data captured at these visits fall within the protocol defined visit windows (Protocol Table 5-1) and there was no corresponding endpoint data collected at the same scheduled visit. The information collected during unscheduled visits will be presented in the listings labeled as the unscheduled visit.

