10.3 Clinical laboratory evaluations

The following laboratory parameters are measured within the study:

- Hematology parameters: Hematocrit, Hemoglobin, Platelets, Red Blood Cells, White Blood Cells, and differential count and percentile (Lymphocytes, Basophils, Eosinophils, Monocytes, Neutrophils)
- Liver Function Tests and other Chemistry parameters: Alanine Aminotransferase (ALT), Aspartate Transaminase (AST), Albumin, Alkaline Phosphatase (ALP), Bicarbonate, Blood Urea Nitrogen, Calcium, Chloride Creatinine, Ferritin, Gamma-glutamyl transferase, Glucose, Iron Binding Capacity Total, Iron Binding Capacity Unsaturated, Lactate Dehydrogenase, Potassium, Phosphorus, Serum Iron, Sodium, Total cholesterol, Total bilirubin, Total protein, Transferrin, Uric acid
- Endocrine parameters: Estradiol (females only), Follicle-stimulating Hormone (FSH), Insulin-like Growth Factor 1 (IGF-1), Luteinizing Hormone (LH), Progesterone (females)

only), Prolactin, Testosterone (males only), Thyroxine Free (T4FR), Triiodothyronine (T3), Thyroid Stimulating Hormone (TSH)

– Endocrine normal ranges are provided by the central lab and included in the dataset specifications.

- Urinalysis: Color, Appearance, Glucose, Protein, Blood, Ketones, Urine Pregnancy Test

Summary statistics of the observed values and their change from Baseline and the frequency of abnormal values based on normal ranges will be presented by visit for laboratory parameters of hematology, chemistry and endocrinology.

Laboratory data outside the reference range will be highlighted with “L” for low and “H” for high in all laboratory subject data listings where applicable. Individual subject data listings will be presented for laboratory parameters of hematology, chemistry and endocrinology. Urinalysis and pregnancy test results will only be listed.

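### Laboratory abnormalities are counted only by visit, most unscheduled results are left out, and the protocol's by-arm presentation of clinically significant abnormalities has no SAP table

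*SAP*

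**What the plan says.** **Laboratory table.** SAP 10.3 plans summary statistics and one abnormality summary: "the frequency of abnormal values based on normal ranges will be presented by visit for laboratory parameters of hematology, chemistry and endocrinology". It plans no count of subjects abnormal at any time after Baseline and no table of clinically significant values. Urinalysis is only listed.

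**Unscheduled results.** SAP 3.2.3 states that "assessments at unscheduled visits will not be considered in the by-visit analysis unless data captured at these visits fall within the protocol defined visit windows". The exception has a second condition, that "there was no corresponding endpoint data collected at the same scheduled visit". The windows meant are those of Protocol Table 5-1, not the wider ones that SAP 3.2.3 uses to identify important protocol deviations. The results remain visible elsewhere: "The information collected during unscheduled visits will be presented in the listings labeled as the unscheduled visit". AEs are not restricted to visits: "Information collected in the log forms (e.g., AEs and concomitant medications) is included in the analysis".

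**Protocol output.** Protocol 13.4.1 summarises change from Baseline in laboratory data by visit and arm. For abnormalities it drops the visit: "Post-Baseline clinical significant abnormalities will be presented by treatment group".

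**Early termination.** SAP 1 and 3.9 say that the analyses are cut back because the study stopped early, that all data will be listed and that key summary tables will be produced. Neither section says which laboratory outputs are dropped.

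**The concern.** An investigator who orders an extra laboratory test often has a reason for it, so unscheduled results are not a random sample of all results. A table that leaves most of them out can undercount abnormal subjects where something prompted testing. Safety and tolerability are the secondary objective (SAP 2.1.2), and the by-arm laboratory table is where a reader would compare the groups.

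The protocol also promised a by-arm presentation of clinically significant abnormalities. Without a table, a reader has to assemble it from listings. Without an entry in SAP 3.9, the reader cannot tell whether it was dropped on purpose.

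**Working it through.** The plan states no figure to reproduce. The check compares texts and counts days.

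**1. When on-treatment laboratory values are scheduled.** Visits are taken from Protocol Section 8, because the column layout of Table 5-1 is not reliable in the text used here.
- Safety laboratory tests: Visit 6 (Day 22, section 8.3.1) and Visit 9 (Day 106, section 8.3.3). Section 8.3.2 lists none at Visits 7 and 8. The gap is 106 − 22 = 84 days.
- Hormone status: Visit 9 only.
- A later draw at Safety Follow-Up applies only to subjects who do not enter RL0007 (section 8.5).

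**2. Which days the window exception can reach**, out of treatment Days 1 to 110. Visit 6 is taken at ±2 days, as in Protocol 8.3 and SAP 3.2.3.

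| Windows admitted | Days covered | Days outside |
|---|---|---|
| Visits 6 and 9: Days 20–24, 104–108 | 5 + 5 = 10 | 100/110 = 90.9% |
| Same, Visit 6 at ±1 day | 3 + 5 = 8 | 102/110 = 92.7% |
| Hormones, Visit 9 only | 5 | 105/110 = 95.5% |
| Visits 4 to 9: Days 7–9, 14–16, 20–24, 48–52, 76–80, 104–108 | 3 + 3 + 5 + 5 + 5 + 5 = 26 | 84/110 = 76.4% |

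The last row is the generous reading, in which a result inside the window of a visit without planned laboratory tests still counts. Adding Days 1 and 110 as single days gives 28 covered and 82 outside. Taking Visit 6 at ±1 day without those two days gives 24 covered and 86 outside.

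Inside a laboratory-visit window, an unscheduled repeat is still left out whenever the scheduled value exists.

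**3. A hypothetical subject followed through the rules.** Hemoglobin is in range on Day 22, below range at an unscheduled visit on Day 60, and in range on Day 106.
- By-visit table: Day 60 lies between the Visit 7 window (48–52) and the Visit 8 window (76–80), so the value is left out. The subject is not abnormal at Visit 6 or Visit 9.
- Listing: the value appears, flagged low.
- TEAE tables: the subject appears only if the finding was reported as an AE.
- Protocol 13.4.1 output, if the value is judged clinically significant: the subject should be counted, but no SAP table does so.

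**4. What one omitted subject is worth.** The count falls by 1 and the percentage by 100/n points. At 138/3 = 46 per arm (equal allocation assumed) this is 2.2 points. The study stopped early and arm sizes are not given. With 23 per arm, assumed for illustration, it is 4.3 points.

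**The case against.** The strongest reply is that the safety output as a whole does not depend on this table.

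- **Liver signals.** Protocol 6.3.1 says "Subjects with PDILI should not be withdrawn from the study until investigation and monitoring are complete". Monitoring normally runs until values normalise, stabilise or return to baseline, so the withdrawal-visit value may be the recovered one. A reader might infer that a liver signal between visits enters no summary. The documents do not support that. Protocol 11.6.1 requires every PDILI event to be reported as an AE, AE data are analysed whatever the visit, and SAP 10.2 tabulates TEAEs. SAP 10.3.1 adds a listing of elevated liver tests that includes potential Hy's Law cases at any time during exposure. The numeric peak may be absent from the by-visit table, but the event still reaches a by-arm table. This part of the objection stands in full.
- **Other abnormalities.** Protocol 11.1.1.1 counts an abnormal laboratory finding among possible AEs, so a clinically significant one would ordinarily be reported. This stands in part. Reporting rests on the investigator's judgement, and Protocol 11.1.2.1 prefers the overall diagnosis to individual signs. A TEAE table is therefore not a count by laboratory parameter.
- **Declared cut-back.** SAP 1 and 3.9 give general notice of a reduced analysis. That explains a shorter output, but a laboratory abnormality frequency was kept and the protocol's by-arm output is not named as dropped.
- **Size.** The percentages above are shares of calendar days, not of abnormalities missed. An abnormality still present at the next scheduled visit is counted, and SAP 4.2 carries withdrawal data to the next scheduled visit. Only abnormalities that have resolved by then are missed. This stands.

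The by-visit rule is not an error in itself. It suits a table of values over time.

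**Conclusion.** The concern holds as a limited reporting gap. Followed as written, the by-arm laboratory table can omit abnormalities found between Visit 6 and Visit 9. The protocol's presentation of clinically significant post-Baseline laboratory abnormalities by treatment group has no SAP table and is not listed among the changes in SAP 3.9.

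It mainly affects hematology, endocrine and non-liver chemistry values, which reach a by-arm table from an unscheduled visit only if reported as AEs. The exclusion is not absolute: an in-window result counts when the scheduled visit has none. Between 82 and 102 of 110 treatment days lie outside the reach of that exception for safety laboratory tests, and 105 lie outside the Visit 9 window for hormones. These figures show how narrow the exception is. They do not show how many subjects are missed, which cannot be derived from the documents.

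The conclusion assumes that the laboratory visits are those in Protocol Section 8 and that the 3.2.3 rule, which is worded generally, applies to laboratory data.

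**What to change.** In SAP 10.3, keep the by-visit rows. Add, by treatment group, the number and percentage of subjects with at least one post-Baseline abnormality at any scheduled, unscheduled or repeat assessment, for each hematology, chemistry and endocrine parameter. The denominator is subjects with at least one post-Baseline value. State that the unscheduled-visit exclusion in SAP 3.2.3 does not apply to these rows.

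Choose the criterion openly. Protocol 13.4.1 asks for clinically significant abnormalities, but neither document says how a laboratory value is judged so; if this criterion is used, the SAP should say where the judgement comes from. If the normal range already in SAP 10.3 is used instead, record the substitution in SAP 3.9 and show low and high separately. If no table is added, SAP 3.9 should at least name the protocol output as dropped.

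The cost is a few SAP sentences and extra rows per parameter. With the normal-range criterion, the data are already collected and listed. The downside is that subjects tested more often have more chances to be flagged, so the rows need a footnote saying so.

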3.3 Definition of Baseline values

Unless otherwise noted, baseline is defined as the last available value on or before the day of the first patch application.

3.4 Protocol deviations

Important protocol deviations are deviations from the protocol which potentially could have a meaningful impact on study conduct or on the primary efficacy, key safety, or PK outcomes for an individual subject. The criteria for identifying important protocol deviations will be defined within the appropriate protocol-specific document. Important protocol deviations will be reviewed as part of the ongoing data cleaning process and data evaluation. All important deviations will be identified and documented prior to unblinding.

3.5 Analysis sets

Six analysis sets will be defined for this study.

3.5.1 Enrolled Set (ES)

The ES will consist of all subjects with a signed informed consent form and any demographic data.

3.5.2 Randomized Set (RS)

The RS will consist of all subjects from the ES who have been randomized.

3.5.3 Safety Set (SS)

The SS will consist of all subjects from the RS who have at least one patch (rotigotine or placebo) applied. This population will be used for safety analysis.

3.5.4 Full Analysis Set (FAS)

The FAS will consist of all subjects from the SS who have a valid IRLS score with a valid post-Baseline IRLS score or a valid CGI Item 1 score at Baseline paired with a valid post-Baseline CGI Item 1 score. This population is the primary population for efficacy analysis.

A valid IRLS or CGI Item 1 score at Baseline is defined as a completely answered questionnaire on or before the date of first study medication. A valid post-Baseline IRLS or CGI Item 1 score is defined as a completely answered questionnaire during the Treatment Period, i.e., measured after Baseline and on or before one day after the last patch removal.

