9.1 International Restless Legs Rating Scale (IRLS)

The IRLS will be performed at Screening, Baseline (Visit 2), Visit 6, Visit 7, Visit 8, and Visit 9. The IRLS should also be performed in the event that a subject is prematurely withdrawn from the study (Withdrawal Visit).

The IRLS was developed by the International RLS Study Group and was validated in a large-scale study (Walters et al, 2003). The IRLS is intended to evaluate, in a standardized way, the subjective intensity of major symptoms of RLS and, in 2 items (9 and 10), the impact of the disease on subjects' functioning in daytime activities by use of a 5-point scale for each of a total of 10 items:

1. Discomfort in arms and legs due to RLS
2. Urge to move
3. Relief of symptoms by movement
4. Sleep disturbances due to RLS
5. Fatigue and somnolence during the day due to RLS
6. Global severity rating of RLS
7. Frequency of symptoms
8. Severity of symptoms (if present) during an average day (24 hours)
9. Impact of symptoms on daytime activities (family, home, social, job)
10. Impact of symptoms on mood (eg, angry, depressed, sad, anxious, irritable)

Each item is scored by the subject. Investigators or clinic personnel can assist the subject if he/she has difficulty understanding the items or locating the appropriate score. Scores for each item range from 0 (not present) to 4 (very severe). A sum score of all 10 items is calculated for analysis. The sum score ranges from 0 (no RLS symptoms present) to 40 (maximum severity in all symptoms).

The following ranges are used to determine severity categories:

- 0=none
- 1 to 10=mild
- 11 to 20=moderate
- 21 to 30=severe
- 31 to 40=very severe

A minimum score of 15 points (moderate) is typically required for inclusion in a study at Baseline.

Subjects should answer each item in reference to the 7 days prior to their visit. If the timeframe since the last visit is <7 days (eg, in the event of premature discontinuation), the subject should answer each item in reference to the days since their last visit.

Subjects will be classified into the following categories:

- IRLS responder: A relative reduction in IRLS total score in percentage points at the end of maintenance compared to Baseline. This categorization will be carried out for a reduction of at least 50% (that is a percentage relative change for less than or equal to -50%),

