13.3 Planned efficacy analyses

13.3.1 Analysis of the co-primary efficacy variables

Mean changes from Baseline to the end of the Maintenance Period in IRLS sum score and CGI (Item 1) in the 2 rotigotine arms (2mg/24h and 3mg/24h) will be compared with placebo to demonstrate superior efficacy of rotigotine.

The primary analysis of each co-primary variable will be based on a mixed model repeated measures (MMRM) analysis of covariance (ANCOVA) that includes terms for treatment group, visit, the respective Baseline score, and the interaction between treatment group and visit. The model will define patient as a random effect and utilize an unstructured covariance pattern. From this MMRM ANCOVA, treatment least-square (LS) means (with 95% confidence intervals [CI]) will be calculated and 1-sided 2 sample t-test will be performed (significance level 0.025) to test

the superiority of the rotigotine dose levels versus placebo, starting with 3mg/24h. The corresponding p-values will also be calculated.

The null hypotheses at each dose level are (H0): rotigotine is not superior compared to placebo. The alternative hypotheses are (H1): rotigotine is superior to placebo. Both co-primary endpoints must demonstrate significant results (at significance level 0.025) to demonstrate superiority of this dose level of rotigotine over placebo.

If the 3mg/24h dose is successful, the 2mg/24h dose level will be tested in the same way. Since both hypotheses have to be rejected in order to continue, multiplicity adjustment is not needed for the 2 hypotheses at each dose level. The multiplicity based on the two dose levels will be covered by applying the hierarchical approach (closed test procedure).

For subjects who prematurely withdraw for any reason before end of Maintenance, data collected during the Withdrawal Visit will be used to impute measurements at the next consecutive visit.

IRLS or CGI-1 measurements must be performed no longer than 1 day after the last patch removal to be utilized for analysis (valid measurements).

The above analyses will be performed on the FAS and the PPS. The primary analysis will be considered the analysis on the FAS.

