3.2.1.2 Date of last patch removal

The date of last patch application is documented on the Study Termination page of the eCRF. If the date of last patch application on this page is missing the last available kit start date on the Drug Accountability log form will be used as the date of last patch application. Thus, the date of the last patch removal is defined as the date of the last patch application + 1.

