3.2.2 Study periods

The following time periods are defined for this study.

- Screening Period:

The Screening Period starts with Visit 1 and ends the day before the date of the first patch application. This period includes Visit 2/Day 0 at which the subjects are randomized, and study medication is assigned and shipped.

- Titration Period:

The Titration Period starts at the day of the first patch application (Day 1) and ends on the day prior to Visit 6. In case of a premature withdrawal before Visit 6, the Titration Period ends at the day of the Withdrawal Visit. If the Withdrawal Visit is missing or the date of the last patch removal (or last known patch removal) is before the Withdrawal Visit, the Titration Period ends at the day of last patch removal.

- Maintenance Period:

The Maintenance Period starts at Visit 6 and ends at Visit 9. If the subject withdraws prior to Visit 9, the Maintenance Period ends at the day of the Withdrawal Visit date or the last patch removal date (or last known patch removal date), whichever is earlier.

- Taper Period:

The Taper Period starts at the date of last maintenance patch removal and ends at the day of last patch removal. If the day of last patch removal is on the date of last maintenance patch removal, i.e., no de-escalation was performed for any reason, then no Taper Period is defined for this subject.

- Treatment Period:

The Treatment Period comprises the Titration Period, the Maintenance Period, and the Taper Period, i.e., it starts with the day of first patch application and ends on the maximum end date of the Titration, Maintenance and Taper periods.

- Safety Follow-Up Period:

The Safety Follow-Up Period starts the day after the end of the Treatment Period and ends at the date of the Safety Follow-Up Visit. However, AEs starting within 30 days following the date of last patch removal will be considered for analysis, even if the start date is after the

date of last study assessment. If the subject rolls over into the RL0007 study, then the Safety Follow-up Period dates will be missing.

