4.2.1 Missing efficacy data

For subjects who prematurely withdraw for any reason before EoM, values for planned efficacy assessments scheduled at subsequent visits will not be imputed. Efficacy assessments must be performed no later than 1 day after the last patch removal to be utilized for analysis (valid measurements).

For IRLS analysis, if any item is missing, the IRLS sum score will not be calculated. Missing IRLS baseline items and therefore the total score will be regarded as an important protocol deviation.

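### The IRLS/CGI Item 1 validity window does not exclude the Taper, so a score taken after dose reduction has begun can, by exception, be summarised as End of Maintenance

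*SAP*

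**What the plan says.** **Validity.** SAP 3.5.4 requires a complete questionnaire in the Treatment Period, which it spells out as "measured after Baseline and on or before one day after the last patch removal". SAP 4.2.1 applies the same limit to all efficacy data: "Efficacy assessments must be performed no later than 1 day after the last patch removal to be utilized for analysis". Protocol 13.3.1 agrees for the co-primary scales: "IRLS or CGI-1 measurements must be performed no longer than 1 day after the last patch removal".

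**Which patch.** In SAP 3.2.1.2 "the date of the last patch removal is defined as the date of the last patch application + 1", with no restriction to maintenance patches. SAP 3.2.2 adds that "The Treatment Period comprises the Titration Period, the Maintenance Period, and the Taper Period". The same section starts the Taper at a separately named date, the last maintenance patch removal. The SAP therefore has the distinction available but does not use it in the validity rule.

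**Dose in the Taper.** Protocol Table 7-3 takes subjects on 3 mg/24h to 2 mg and then 1 mg, and subjects on 2 mg/24h to 1 mg. Subjects on 1 mg (back-titrated) and on placebo do not change.

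**Visit assignment.** SAP 3.2.3 follows the eCRF visit label with no re-windowing. It leaves unscheduled assessments out of by-visit summaries "unless data captured at these visits fall within the protocol defined visit windows" and the scheduled visit has no such data. SAP 4.2 assigns off-schedule withdrawal data to the next scheduled visit.

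**Recall period.** Protocol 9.1 uses a 7-day recall for the IRLS. If the last visit was less than 7 days ago, "the subject should answer each item in reference to the days since their last visit".

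**The concern.** The co-primary variables are changes to the end of Maintenance, when subjects are meant to be on their assigned or back-titrated dose. A score given during the Taper reflects a lower dose for anyone on 2 or 3 mg/24h. The shortened IRLS recall makes this sharper: a questionnaire completed a few days after Visit 9 asks about the taper days and not about the last week of Maintenance.

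If such a score is summarised as EoM, it can dilute an active arm's mean but not the placebo mean. It could also bring a subject into the FAS with no on-dose efficacy measurement at all.

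**Working it through.** **Inputs.** Visit 9 is Day 106 ± 2, so Days 104 to 108 (Protocol Table 5-1). The Taper lasts up to 4 days from the day after Visit 9 (Table 5-1 notes; Protocol 8.4). Last removal is last application + 1 day (SAP 3.2.1.2). Assumptions: a maintenance patch is applied on the day of Visit 9, and the full taper is taken.

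**Formulas.** With Visit 9 on Day V:
- taper patches: Days V+1 to V+4
- last removal: V+4+1 = V+5
- window closes: V+5+1 = V+6
- days open to the unscheduled route: days after V and up to Day 108, so 108 − V

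For V = 106 the taper patches fall on Days 107 to 110, which reproduces the days in Table 7-3.

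| Visit 9 | Taper patches | Last removal | Valid to | Days exposed by the unscheduled route |
|---|---|---|---|---|
| 104 | 105–108 | 109 | 110 | 4 |
| 105 | 106–109 | 110 | 111 | 3 |
| 106 | 107–110 | 111 | 112 | 2 |
| 107 | 108–111 | 112 | 113 | 1 |
| 108 | 109–112 | 113 | 114 | 0 |

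**Routes into the EoM summary.** IRLS and CGI Item 1 are last scheduled at Visit 9 (Protocol 9.1 and 9.2), and Visit 10 has neither. Three exceptions remain.

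- (a) *Unscheduled score.* Visit 9 has no score and one is taken at an unscheduled contact up to Day 108. Example: Visit 9 on Day 104 without an IRLS, then an IRLS on Day 108. It is valid (the window runs to Day 110) and inside the visit window. Its recall covers Days 104 to 108, and the taper patches were applied on Days 105 to 108.
- (b) *Late score on the Visit 9 page.* The eCRF label governs, so the Day 108 limit does not apply. Only the validity window does, which is Day 112 for V = 106.
- (c) *Withdrawal after Visit 8.* Protocol 8.7 lets an Unscheduled Visit dispense taper medication and lists neither IRLS nor CGI there. A Withdrawal Visit held after tapering has begun still gives a valid score, and the next scheduled visit is Visit 9.

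**FAS.** Neither scale is scheduled between Baseline and Visit 6. For a subject who withdraws in Titration, one Withdrawal Visit score may be the only post-Baseline value. If it is taken after tapering began, it alone decides membership.

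**Internal mismatch.** SAP 3.5.4 equates the window with the Treatment Period. For V = 106 that period ends at last removal (Day 111), while the window runs to Day 112.

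**Size.** If a share p of an active arm's EoM scores is taper-time and a share L of the planning effect of 5.9 IRLS points (Protocol 13.8) is lost in them, the shift is p × L × 5.9. The documents give neither p nor L. Each could lie anywhere from 0 to 1, so no useful figure follows.

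**The case against.** Validity is not visit assignment. The window only caps which scores may be used. SAP 3.2.3 and 4.2 decide which visit they belong to, and no rule sends taper scores to EoM as a matter of course. That stands, and it limits the point to exceptions.

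Each exception is narrow:
- Route (a) needs an empty Visit 9, a scale that the protocol does not list for unscheduled visits, and a date no later than Day 108. With Visit 9 on Day 106 that leaves Days 107 and 108, when Table 7-3 has the 3 mg/24h arm on 2 mg. Protocol 13.8 assumes similar effects at 2 mg/24h, so on that assumption little is lost in that arm on those days.
- Route (c) is unusual. The Withdrawal Visit has Visit 9 procedures (Protocol 8.6), which include both the scales and taper dispensing, so scoring normally comes first. Withdrawals before Visit 8 do not reach the EoM summary.
- FAS entry on a taper-time score requires that the subject has no other valid post-Baseline score.

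A reader might take the Amendment 1 entry in the SAP appendix, on efficacy endpoints collected after a visit at an unscheduled visit, as proof that taper-time scoring was foreseen. The entry is general and does not mention the Taper.

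The current SAP also summarises efficacy only descriptively by visit (8.1.2), and listings label unscheduled data as such. That stands too. None of it removes the gap: nothing in either document excludes a taper-time score from these routes.

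**Conclusion.** The gap is real but limited. The validity window ends one day after the last patch of any kind, so it admits taper-time scores, and three exceptions can carry one into the EoM summary. The unscheduled route exposes 4 to 0 days, depending on the date of Visit 9. Dilution, if any, is one-sided, because only subjects on 2 or 3 mg/24h have a dose reduction. The day counts rest on a full four-day taper and on a maintenance patch being applied on the day of Visit 9.

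Three stronger readings are not supported:
- *Taper scores are EoM data by rule.* None are scheduled, and entry is by exception only.
- *Unscheduled scores up to Day 112 count as EoM.* That route closes on Day 108.
- *A test of rotigotine against placebo is biased by a stated amount.* The documents give no frequency or loss of effect, and the operative SAP runs no efficacy test. Only descriptive means are affected. The point would weigh more under the MMRM in Protocol 13.3.1, which carries the same limit.

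**What to change.** State one cut-off in SAP 3.5.4 and 4.2.1, and in Protocol 13.3.1:

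- For subjects who enter the Taper, IRLS, CGI Item 1 and RLS-6 scores count for FAS membership and for by-visit and EoM summaries only if taken before the first taper patch is applied. Later scores are listed only, whether recorded on the Visit 9 page or at an unscheduled or Withdrawal Visit.
- For subjects who stop without tapering, keep the present limit of last patch removal plus 1 day.

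Moving the anchor to the last maintenance patch removal plus 1 day would not be enough. For Visit 9 on Day 106 that gives 107 + 1 = Day 108, which still admits both days exposed by the unscheduled route.

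Also align the Treatment Period wording in SAP 3.5.4 with the window, since the period includes the Taper and ends a day earlier.

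The cost is a short text change in two SAP sections and one protocol section, plus one programming flag. The downside is that a few late-captured scores become missing.
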